### 20.3 Description of Statistical Methods

### 20.3.1 General Approach

We recognize that the relatively small sample sizes proposed in the RCT are not likely to produce statistical significance, unless the effect sizes are remarkably high. We will carry out a full Mixed Model Repeated Measures (MMRM) statistical analysis in case CBD does perform so well. However, the main focus of the statistical analysis of the results of the trial will be to characterize the effect sizes and response rates across the various measurement domains and the profiles of individuals who are treatment successes. The intent to treat (ITT) population will contain all randomized patients who receive at least one dose of double-blind study medication and from whom at least one post-baseline (B1) efficacy measurement is obtained while on study medication. The efficacy analysis will be based on the ITT population. Two-sided hypothesis testing will be utilized. Tests with p-values less than or equal to 0.05 will be considered statistically significant, while those less than equal to 0.10 will be considered suggestive. Since this trial is the first use of this treatment for this diagnostic indication, no adjustments of p-values for multiple comparisons will be made. Thus, all control of type 1 error is contrast-wise. All confidence intervals will be two-sided with 95% confidence. Mean treatment effect, standard errors, and 95% confidence intervals will be derived from fully adjusted models on outcomes averaged across the treatment period. Cohen's d and p-values will be calculated from fully adjusted models with appropriately transformed outcome variables. For dichotomous drinking outcomes, prevalence rates will be calculated. Odds ratios (ORs) and p-values will be derived from logistic regression models including treatment group.

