#### 4.2.2 Secondary Study Endpoints Secondary Alcohol use endpoints

Secondary efficacy endpoints are the percent carbohydrate-deficient transferrin (CDT); the percentage of heavy drinking days (four or more drinks for women or five or more drinks for men per drinking day) averaged for each treatment week; weekly average severity of alcohol craving assessed by the Penn Alcohol Craving scale [79]; weekly percentage of very heavy drinking days (8+/10+ drinks per day for women and men respectively); weekly percentage of days abstinent; weekly percentage of subjects with no heavy drinking days, and weekly percentage of subjects that are 'present and clean', i.e. present to provide breath alcohol levels (BAC) and have a BAC of zero [80].

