### 7.3.2 Enrollment/Baseline (B1) (Day 0, 1-30 days after Screening Visit)

- Perform alcohol breathalyzer to obtain BAC
- Record vital signs, results of examination, other assessments, concurrent medications and menstrual calendar (if applicable)
- Record AUD-related and PTSD related measures
- Collect imagery scripts for the cue/traumatic stress response task
- Collect urine for urine drug analysis and urine pregnancy test (if applicable)
- Collect baseline plasma for baseline CBD, THC, and AEA levels (pre-CBD dosing levels)
- Collect blood for carbohydrate deficient transferrin (CDT) test
- Record results of evaluations of safety and psychomotor effects and AUD, PTSD related domains
- Record adverse events as reported by participant or observed by investigator
- Evaluate and record alcohol use
- Administer medical management session
- Provide participants with study medication to administer at visit
- Provide participants with sufficient study medication to administer daily until the next scheduled visit (1 week), and instructions for how to use the study medication and document their use

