### 20.3.2 Analysis of the Primary Endpoint(s)

For Hypothesis 1a, Safety and tolerability, the frequency of adverse events will be analyzed for the entire sample at all time points, tabulated for each treatment group, and compared using chi-squared tests. The safety analysis will be largely descriptive of outcomes for the entire study population. The incidence of AEs will be summarized by system organ class, preferred term, the likelihood of its relationship to the treatment, and severity for each treatment group. Clinical laboratory data will be summarized by type of test. Frequency and percentage of patients whose values fall outside of reference ranges will be presented for each measurement.

For Hypothesis 1b, Alcohol Use. The Primary outcome measure, number of drinks per day, will be analyzed with an MMRM to assess differences in change from baseline. The primary contrast is change from baseline (B1) at week 6 (T8). The model at each time point will include terms for treatment, time and treatment by time interaction as factors and the baseline value for each score as a covariate. Parameter estimation will be based on REML and to begin an unstructured covariate matrix will be used. If the model fails to converge, the form of the covariance matrix will be chosen based on Akaike's Information Criteria, and Schwarz' Bayesian Criterion. Model-based LS means will be obtained for change from baseline to each time point for each treatment group. At each time point, contrasts between CBD and placebo will be obtained. Secondary alcohol use measures will be tested with MMRM sequentially in a closed testing union intersection paradigm in the order listed in section C.8.3. Validity of the p-value will extend until the first test fails to have a p-value smaller than a two-sided alpha of 0.05. The analyses will continue for all measures but the resulting p-value will be nominal.

For Hypothesis 2, PTSD symptoms, the primary outcome measure, total score of the PCL-5, will be analyzed in the same way as the primary outcome for alcohol use. The primary contrast is change from baseline (B1) at week 6 (T8).

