### 20.3.6 Baseline Descriptive Statistics

Treatment groups will be compared on several baseline characteristics, including sex, age, race/ethnicity, education level, baseline measures of alcohol consumption (% drinking days and % heavy drinking days), alcohol craving (PACS), anxiety (BAI), mood (BDI-II), CAPS total, and self-efficacy (AASE). Categorical data will be tallied, and means and standard deviations of continuous scores will be calculated.

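### Dichotomous drinking outcomes have two stated methods: a logistic model that names no baseline covariate, and an MMRM unsuited to 0/1 data. One logistic-type model with one continuous baseline drinking measure would serve better

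*Combined protocol and SAP*

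**What the plan says.** Section 4.2.2 lists two measures among the secondary alcohol endpoints that are yes/no for each participant in each week: "weekly percentage of subjects with no heavy drinking days, and weekly percentage of subjects that are 'present and clean", the latter meaning present for a breath test with a reading of zero.

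The protocol gives two rules for analysing them.

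- **Section 20.3.1.** Prevalence rates are reported for dichotomous drinking outcomes, and then: "Odds ratios (ORs) and p-values will be derived from logistic regression models including treatment group". No other term is named, and nothing is said about week or repeated measures. For mean treatment effects, the same paragraph says that estimates "will be derived from fully adjusted models on outcomes averaged across the treatment period", and Cohen's d also comes from fully adjusted models.
- **Section 20.3.2.** Secondary alcohol measures, without exception, will "be tested with MMRM sequentially in a closed testing union intersection paradigm". The MMRM described just before is fitted by REML to change from baseline and includes "the baseline value for each score as a covariate".

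Baseline drinking is available. The B1 visit in section 7.3.2 includes the item "Evaluate and record alcohol use", and section 20.3.6 compares the groups on percent drinking days and percent heavy drinking days. Section 20.1 defers a formal SAP to before database lock and unblinding.

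**The concern.** The same two endpoints can be analysed in two ways, which give different effect measures and different p-values: an odds ratio from the logistic model, and a difference in mean change from the MMRM. The sequential procedure in section 20.3.2 needs one defined p-value per endpoint.

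Neither route uses baseline drinking well. The logistic route names no baseline term. The MMRM route uses the baseline value of the outcome itself, which tells little for "weekly percentage of subjects with no heavy drinking days": section 5.1 requires at least 4 heavy drinking days in the 30 days before screening, so over that window nobody has the favourable value at entry. A shorter baseline window could vary, but none is defined.

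At stake is how much 48 participants can say about response rates, which section 20.3.1 names as part of the main focus of the analysis.

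**Working it through.** **The plan's own figure.** The documents give no rate, effect or power for a binary drinking outcome. The only power figure, d = 0.939 for 0.80 power in section 20.4, is for a t test. At 30 versus 18 with two-sided 0.05 the t test needs d = 0.853; 0.939 is reproduced at 25 versus 15. That mismatch does not bear on this point.

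**Inputs.** From the protocol: 30 on CBD, 18 on placebo, two-sided 0.05. Assumed, since the documents are silent: response rates of 50% versus 20% (other pairs below) and the strength of the baseline covariate.

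**Unadjusted analysis by hand.**

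- Marginal odds ratio: (0.5/0.5) / (0.2/0.8) = 4.0.
- SE of log OR: √(1/15 + 1/15 + 1/3.6 + 1/14.4) = √0.4806 = 0.693.
- SE of risk difference: √(0.25/30 + 0.16/18) = √0.01722 = 0.131.
- Pooled rate: (15 + 3.6)/48 = 0.3875. Null SE: √(0.3875 × 0.6125 × (1/30 + 1/18)) = 0.1452.
- Power: Φ[(0.30 − 1.96 × 0.1452)/0.1312] = Φ(0.117) = 54.6%.

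**Adjusted analysis by simulation.** The model is logit P(Y=1) = a + b·treatment + g·X, with X a standardised baseline measure. The values of a and b are set so that the marginal rates stay at 50% and 20% whatever g is. There were 4,000 trials per setting, with likelihood-ratio tests with and without X. The standardised risk difference averages the fitted probabilities over all participants under each arm. Relative efficiency is (SD unadjusted / SD adjusted)².

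| g (log OR per SD) | Power without → with X | SE of log OR with X (0.69 without) | Conditional OR | SD of risk difference without → with X | Relative efficiency |
|---|---|---|---|---|---|
| 0 | 55% → 57% | 0.73 | 4.0 | 0.1307 → 0.1322 | 0.98 |
| 0.5 | 57% → 61% | 0.74 | 4.3 | 0.1309 → 0.1289 | 1.03 |
| 1.0 | 58% → 66% | 0.81 | 5.2 | 0.1298 → 0.1217 | 1.14 |
| 1.5 | 58% → 73% | 0.91 | 6.8 | 0.1314 → 0.1157 | 1.29 |

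A further run of the same design gave 58–59% rising to 61%, 68% and 74%, with efficiencies of about 1.04, 1.14 and 1.25.

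At g = 0.5, 1.0 and 1.5, other rate pairs give:

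- 40% versus 20%: 31 → 33%, 30 → 37%, 31 → 43%.
- 60% versus 20%: 82 → 84%, 82 → 87%, 83 → 92%.

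At g = 1.0 the gain is worth 48 × 0.14 ≈ 7 further participants.

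**Test size and penalty.** With 30% in both arms (2,000 trials per setting), the unadjusted likelihood-ratio test had size 5.6–6.1%, the adjusted test 6.0–6.6%, and a Firth-penalised adjusted test 4.5–4.7%. At 50% versus 20%, the penalised test had power of 56%, 61% and 67% for g = 0.5, 1.0 and 1.5, against 56% unadjusted. The penalty therefore holds the size but keeps only part of the gain. Separation or extreme estimates occurred in about 0.5–2% of simulated trials, which argues for a single covariate.

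**The MMRM route.** A 0/1 outcome has variance p(1 − p): 0.25 at 50% and 0.16 at 20%. It is tied to the mean, which a normal-theory repeated-measures model ignores.

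**The case against.** Several objections are fair.

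- **Treatment-only is an inference.** Section 20.3.1 says the models include treatment group; it does not rule out covariates, and a formal SAP is still to come. A reader might infer a decision to discard baseline. The documents show only an under-specified model. The wording beside it makes treatment-only the natural reading, and the pending SAP is a reason to settle it now.
- **The MMRM does not drop baseline.** A reader might infer that both routes do. Section 20.3.2 says otherwise; the fault there is the normal model and an uninformative baseline value. It can also be argued that section 20.3.1, as the specific rule, governs binary outcomes, but the protocol does not say so.
- **Adjustment does not tighten the odds ratio.** This stands in full. The SE of the log OR rises from 0.69 to as much as 0.91, and the odds ratio becomes conditional on the covariate. The gain is in power and in the marginal risk difference, which the plan does not currently report.
- **Nothing shows that baseline drinking is strongly prognostic.** This also stands. No baseline-outcome association is given, and none links zero breath alcohol at a visit to baseline heavy drinking.
- **Chance imbalance is not bias.** Correct: under randomisation it is random error that the confidence interval covers.
- **The consequence is small.** The two outcomes come last in section 4.2.2, p-values after the first failed test are nominal, and the protocol itself doubts that significance will be reached.
- **The simulation covers one binary outcome per person.** A weekly repeated-measures version with a penalty was not tested.

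**Conclusion.** The concern holds in limited form. The binary drinking outcomes have two methods that must be reconciled, and the logistic one names no baseline term although suitable measures are collected. With 30 versus 18 participants and assumed rates of 50% versus 20%, one continuous baseline measure adds about 3–4, 8–10 or 15 power points at a log odds ratio of 0.5, 1.0 or 1.5 per SD. Over the rate pairs examined, the standardised risk difference is about 1.01–1.04, 1.12–1.15 or 1.25–1.30 times as efficient. If the covariate is not prognostic there is no real gain and about a 2% loss in efficiency. Unpenalised, the adjusted test has a size of about 5–7%; penalised, the power gain is smaller.

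The documents do not support a claim that the plan is biased, or that a large known gain is being thrown away.

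**What to change.** 1. In section 20.3.2, exempt the dichotomous drinking outcomes from the MMRM sentence, and say how their p-values enter the sequential order.
2. In section 20.3.1, name one logistic-type model per binary outcome, with treatment and one prespecified continuous baseline drinking measure, such as percent heavy drinking days. State the baseline window. Say whether the outcome is weekly or one value per participant; if weekly, allow for within-person correlation.
3. Use a Firth-type penalty, or another small-sample method, as the default where the model allows it.
4. State that the adjusted odds ratio is conditional, and report the standardised risk difference with its 95% confidence interval beside it.

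The cost is wording in the protocol and the pending SAP; no new data are needed. The downsides are the slight size inflation if the penalty is omitted and a small efficiency loss if the covariate proves uninformative. If a weekly model is chosen, its size and convergence with 18 placebo participants should be checked by simulation before the SAP is signed.

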### 20.3.2 Analysis of the Primary Endpoint(s)

For Hypothesis 1a, Safety and tolerability, the frequency of adverse events will be analyzed for the entire sample at all time points, tabulated for each treatment group, and compared using chi-squared tests. The safety analysis will be largely descriptive of outcomes for the entire study population. The incidence of AEs will be summarized by system organ class, preferred term, the likelihood of its relationship to the treatment, and severity for each treatment group. Clinical laboratory data will be summarized by type of test. Frequency and percentage of patients whose values fall outside of reference ranges will be presented for each measurement.

For Hypothesis 1b, Alcohol Use. The Primary outcome measure, number of drinks per day, will be analyzed with an MMRM to assess differences in change from baseline. The primary contrast is change from baseline (B1) at week 6 (T8). The model at each time point will include terms for treatment, time and treatment by time interaction as factors and the baseline value for each score as a covariate. Parameter estimation will be based on REML and to begin an unstructured covariate matrix will be used. If the model fails to converge, the form of the covariance matrix will be chosen based on Akaike's Information Criteria, and Schwarz' Bayesian Criterion. Model-based LS means will be obtained for change from baseline to each time point for each treatment group. At each time point, contrasts between CBD and placebo will be obtained. Secondary alcohol use measures will be tested with MMRM sequentially in a closed testing union intersection paradigm in the order listed in section C.8.3. Validity of the p-value will extend until the first test fails to have a p-value smaller than a two-sided alpha of 0.05. The analyses will continue for all measures but the resulting p-value will be nominal.

For Hypothesis 2, PTSD symptoms, the primary outcome measure, total score of the PCL-5, will be analyzed in the same way as the primary outcome for alcohol use. The primary contrast is change from baseline (B1) at week 6 (T8).

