# **3 Objectives and Purpose**

## 3.1 Primary Objective

The primary objective is to obtain a preliminary assessment of the safety, tolerability, efficacy, and effect size of CBD in reducing self-reported measures of alcohol use and PTSD symptoms in the AUD+PTSD/subthreshold PTSD population.

We predict that treatment with 600mg CBD daily will be well tolerated with no greater psychomotor or other motor side effects compared to treatment with placebo. We predict that CBD will be associated with a greater reduction in drinks per day and PTSD symptoms (total PCL-5 score) compared to placebo.

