# **10 General Guidelines**

All AEs, regardless of causality or severity, must be immediately recorded on the AE CRF when volunteered by the subject or solicited through a study assessment questionnaire. The CRC will record all AEs, regardless of causality or severity, with start dates occurring any time after informed consent is obtained until 7 (for AEs) or 30 (for SAEs) days after the last day of study participation on the AE case report forms (CRF). Information to be collected includes event description, time of onset, clinician's assessment of severity, relationship to study product (assessed only by those with the training and authority to make a diagnosis), and time of resolution/stabilization of the event.

Any medical condition that is present at the time that the participant is screened will be considered as baseline and not reported as an AE. However, if the study participant's condition deteriorates at any time during the study, it will be recorded as an AE.

Changes in the severity of an AE will be documented to allow an assessment of the duration of the event at each level of severity to be performed. AEs characterized as intermittent require documentation of onset and duration of each episode.

At the last scheduled visit, the CRC should instruct each subject to report any subsequent event(s).

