### 20.3.8 Multiple Comparison/Multiplicity

Because our primary outcomes are safety data, in which we hypothesize a null difference between treatment groups, we will not employ a correction for Type I error/alpha inflation.

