## 20.4 Sample Size

We will phone screen approximately 600 participants, and enroll approximately 150 participants to randomize a total of 48 participants (through week 6/T8). In this pilot study sample sizes are obviously quite limited. A simple t test of mean differences requires an effect size of .939 to have .8 power. We have chosen an unbalanced design with more subjects on CBD to maximize the ability to characterize response to treatment for use in planning future confirmatory trials and still have valid hypotheses tests.

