### 20.5 Measures to Minimize Bias

### 20.5.1 Enrollment/Randomization/Masking Procedures

Enrolled participants that pass screening will be randomized using a 5:3 ratio to receive either 600mg CBD/day (PO) or placebo respectively for 6 weeks (N=30 participants on CBD and N=18 participants on placebo). Treatment assignment will be known only to a designated unblinded study staff member in charge of dispensing study medication under direct PI supervision, but the blind can be broken if necessary, e.g., in case of a serious reaction during drug administration.

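### Safety is a primary outcome with a hypothesised null difference, but the AE comparison is a chi-squared test at 30 v 18 with no margin, no interval and an inconsistent AE window

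*Combined protocol and SAP*

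**What the plan says.** The Protocol Summary lists adverse events among the primary endpoints, and section 3.1 puts safety and tolerability in the primary objective. Section 3.1 also predicts that CBD "will be well tolerated with no greater psychomotor or other motor side effects compared to treatment with placebo". Section 20.3.8 declines any alpha correction because the primary outcomes are safety data "in which we hypothesize a null difference between treatment groups".

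For Hypothesis 1a, section 20.3.2 says that AE frequency "will be analyzed for the entire sample at all time points, tabulated for each treatment group, and compared using chi-squared tests". Section 20.3.4 repeats the chi-squared comparison. Both sections call the safety analysis mainly descriptive and promise incidence tables by arm. Neither gives an interval for the difference between arms, a margin, or the unit of analysis (participants or events).

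The general rules are in section 20.3.1: "Two-sided hypothesis testing will be utilized", and "Tests with p-values less than or equal to 0.05 will be considered statistically significant". Values up to 0.10 are to be called suggestive. Section 20.5.1 gives the arm sizes as "N=30 participants on CBD and N=18 participants on placebo".

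On timing, section 10 records AEs "with start dates occurring any time after informed consent is obtained". Sections 4.2.1 and 7.1.3 instead define the safety assessment by AEs collected at visits after treatment has started.

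**The concern.** A hypothesis of no difference is not supported by failing to reject it. That takes either a margin or an interval narrow enough to exclude differences that matter, and the plan supplies neither for AEs. With 48 participants split 5:3, a test of AE rates can be non-significant while the data remain compatible with a large excess on CBD.

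The window adds to this. Section 7.3.2 places baseline up to 30 days after screening, and section 7.3.6 allows for delays of more than 3 months. If events between consent and first dose enter the arm comparison, they add the same background to both arms and shrink any real difference.

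Both features push towards a finding of no difference on an outcome the plan calls primary. At stake is whether the report can say how large an excess of AEs the trial has ruled out.

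**Working it through.** **The plan's own figure.** The documents give no power or precision figure for AEs. The only power statement is in section 20.4: "A simple t test of mean differences requires an effect size of .939 to have .8 power". It concerns means and does not carry over to AE proportions. It also does not reproduce at 30 v 18, where a noncentral t calculation (two-sided 0.05, power 0.8) gives 0.853; 0.939 corresponds to 25 v 15. The present point does not depend on it.

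**Inputs.** Arms of 30 and 18 (20.5.1); two-sided test, thresholds 0.05 and 0.10 (20.3.1); uncorrected chi-squared with the participant as the unit (assumed, since 20.3.2 does not say). The placebo AE rate is not in the documents, so a range is shown.

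**Power for a threefold rate.** With X ~ Bin(30, 3p) on CBD and Y ~ Bin(18, p) on placebo, power is the sum of P(X = x)P(Y = y) over all tables (x, y) whose chi-squared p-value is at or below the threshold.

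| Placebo v CBD | Power, p <= 0.05 | Missed |
|---|---|---|
| 5% v 15% | 13% | 87% |
| 10% v 30% | 36% | 64% |
| 15% v 45% | 58% | 42% |
| 20% v 60% | 80% | 20% |
| 25% v 75% | 95% | 5% |

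Power crosses 50% at a placebo rate of about 13%, or about 14% with Fisher's exact test and 16% with a continuity correction. At the 0.10 threshold, 10% v 30% is flagged 51% of the time. For a doubled rate, power at 0.05 is 13% for 10% v 20% and 28% for 20% v 40%.

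**What one non-significant result would look like.** Take 9/30 v 2/18, that is 30.0% v 11.1%. Chi-squared = 2.27, p = 0.13. The Wilson limits are 0.167 to 0.479 for CBD and 0.031 to 0.328 for placebo. Newcombe's interval is then:

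- lower: 0.189 - sqrt((0.300 - 0.167)² + (0.328 - 0.111)²) = -0.07
- upper: 0.189 + sqrt((0.479 - 0.300)² + (0.111 - 0.031)²) = +0.38

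The p-value alone hides an interval that runs from 7 points in favour of CBD to 38 points against it.

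**Precision if the true rates are equal.** The approximate 95% half-width is 1.96 × sqrt(p(1 - p)(1/30 + 1/18)): 18 points at p = 10%, 23 at 20% and 29 at 50%.

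**Zero counts.** Hypothesis 1a (section 20.2) predicts that no CBD-related serious AEs will be seen. The exact upper bound for 0/30 is 1 - 0.05^(1/30) = 9.5% (one-sided 95%) or 1 - 0.025^(1/30) = 11.6% (two-sided 95%).

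**Dilution by pre-dose events.** If a share q of each arm has a pre-dose AE, independent of later AEs, the any-AE rate becomes 1 - (1 - q)(1 - p) and the arm difference shrinks by the factor 1 - q. With q = 0.20 (assumed), placebo is 1 - 0.8 × 0.9 = 28% and CBD is 1 - 0.8 × 0.7 = 44%. The difference falls from 20 to 16 points and power from 36% to 18%.

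**The case against.** The strongest reply is that the safety analysis is declared mainly descriptive, that incidence tables by organ class, term, relatedness and severity accompany the test, and that section 20.3.1 concedes that the sample is unlikely to give significance and puts the emphasis on effect sizes. Section 20.1 also promises a formal SAP before lock and unblinding, the usual place for a treatment-emergent definition and an interval method. All of this is fair and lowers the severity. It does not fill the gap: the p-value is still planned, and the intervals in section 20.3.1 come from adjusted models on outcomes averaged over the treatment period, with odds ratios introduced alongside dichotomous drinking outcomes. No interval is assigned to the AE difference.

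Four stronger readings are tempting, and the documents do not support them:

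- A reader might infer that a threefold AE rate would usually go undetected. That depends on a placebo rate the documents do not give. It fails above about 13%, a threefold rate is impossible above 33%, and the 0.10 label flags 10% v 30% about half the time.
- A reader might infer that the prediction of no greater side effects in section 3.1 rests on this test. That prediction concerns psychomotor and other motor effects, and section 20.3.4 gives the field sobriety battery summary statistics only.
- A reader might infer that the plan will take non-significance as proof of safety. No such rule is written. The null difference in section 20.3.8 is offered as a reason for not correcting alpha.
- A reader might infer that pre-dose events are certain to be counted. Section 10 is a recording rule and treats conditions present at screening as baseline. Section 10.1 uses the structured AE questionnaire only after medication, and the time points in section 20.3.2 could mean post-treatment ones. The window is inconsistent, not settled.

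**Conclusion.** The point holds as a weakness in how the safety comparison is specified. A null difference is hypothesised for a primary outcome, chi-squared is the only between-arm AE test named, and there is no margin, no interval for the difference and no treatment-emergent filter. At 30 v 18 a non-significant result cannot support no difference: with equal true rates the interval still spans roughly 18 to 29 points either side for rates between 10% and 50%.

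The power shortfall is conditional. For placebo rates up to about 13%, as might apply to single AE terms, a threefold rate is missed at 0.05 more often than not. For commoner events, or any AE if its placebo rate is higher, the test may do well. These figures assume the uncorrected test, the participant as the unit and all 48 participants analysed. The dilution figures also rest on an assumed pre-dose risk that is equal in both arms and independent of later events.

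**What to change.** In sections 20.3.2 and 20.3.4, and in the formal SAP promised in section 20.1:

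- Compare treatment-emergent AEs only (onset at or after first dose), with the participant as the unit, and list pre-dose events separately. The baseline visit in section 7.3.2 includes both AE recording and on-site dosing, so onset time relative to first dose is needed for that day.
- Report the risk difference with a 95% CI, by Newcombe's method or another suited to small samples, for any AE, related AEs and each common AE.
- Give the exact upper bound wherever the count is zero.
- State that p > 0.05 will not be taken as evidence of equal safety.
- Reconcile section 10 and the time-point wording in 20.3.2 with sections 4.2.1 and 7.1.3, so that recording may start at consent while the comparison starts at first dose.

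This is a cheap improvement. It changes SAP wording and table shells and uses data already collected; section 10 already records time of onset. The downside is that the safety conclusion becomes more cautious.
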